RNA	Ribonucleic acid
SAE	Serious adverse event
SAP	Statistical Analysis Plan
SBP	Systolic blood pressure
SDO	Secure Data Office
SDS	Sheehan Disability Scale
SHBG	Sex hormone-binding globulin
TEAE	Treatment-emergent adverse event
t_{max}	Time to maximum plasma concentration
ULN	Upper limit of normal

Definitions of Terms

BMI	Weight in kilogram divided by the square of height in meters
QTcF	QT interval corrected according to Fridericia's formula: $QTcF = QT/(1000/RR)^{1/3}$
Study drug	All drugs administered during the 12-week treatment period, i.e., the Investigational Medicinal Product (ESN364) and placebo

Study Administrative page removed as out of scope

1. **INTRODUCTION**

1.1 **BACKGROUND INFORMATION**

1.1.1 ***Hot Flashes***

Hot flashes are the most common complaint among women entering menopause and, for many women, may continue to occur for up to 5 years (although about 20% of women may have them for up to 15 years) [1,2,3]. Approximately 75% of perimenopausal women will experience hot flashes, with 10% to 20% of those enduring severe symptoms [4]. Today, more than 25 million women in the United States alone experience symptoms of hot flashes, and 4 million women report severe symptoms [5].

Hot flashes can have a significant negative impact on the quality of life, causing hot flashes to be a major reason for menopausal women to seek medical attention. Despite the vast numbers of individuals affected, the physiology of hot flashes is not fully understood although a disturbance in normal thermoregulatory function is thought to be the main underlying cause.

The primary symptom of hot flashes is a subjective and transient sensation of heat, flushing, and sweating that usually lasts 4 to 10 minutes, and may be accompanied by palpitations, feelings of anxiety, irritability, and, a rare occurrence, panic [2].

The most effective treatment of hot flashes is hormone replacement therapy (HRT), but a Women's Health Initiative study raised questions about the long-term safety of this treatment. Hormone replacement therapy is also the most commonly used pharmacological treatment for hot flashes. However, current guidelines recommend a limited duration of HRT due to associated risks of breast cancer, coronary artery disease, stroke and thromboembolism [1,6]. Furthermore, the current safety data do not support the use of HRT in many patients (e.g., breast/endometrial cancer, liver disease).

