7.5.1.3 BONE DENSITY MARKERS

Plasma concentrations of the bone density markers BALP and CTX will be assessed at Visits 2 and 6.

Blood samples for the assessment of BALP and CTX in plasma will be collected and handled as specified in the central laboratory manual.

After appropriate labeling, the plasma samples will be stored below -70°C at the clinical site. Thereafter, the frozen plasma samples will be transported/shipped on dry ice to the central laboratory (BARC, Gent, Belgium), where they will be collected and kept frozen below -70°C until analysis.

Further procedures for sample collection, shipment, processing, and storage are described in the laboratory manual.

7.5.1.4 *VITAL SIGNS*

Vital sign parameters will be assessed after 5 minutes in supine position at the time points indicated in the [Time and Events Schedule](#).

The vital sign parameters that will be assessed are body temperature (oral), supine systolic and diastolic blood pressure (SBP and DBP, respectively) and pulse rate. These parameters will be measured using a completely automated device consisting of an inflatable cuff and an oscillatory detection system. All values will be registered on a built-in recorder so that measurements are observer-independent.

Any change from baseline in vital sign values occurring during the study that is considered to be clinically relevant or that requires concomitant medication as judged by the Investigator should be recorded in the source documents and the AE section of the eCRF.

7.5.1.5 *ELECTROCARDIOGRAM*

Twelve-lead ECGs will be recorded after 5 minutes in supine position at the time points indicated in the [Time and Events Schedule](#).

The interpretations of the ECGs will be performed by the Investigator or his/her designee at the clinical site. Any change from baseline ECG occurring during the study that is considered to be clinically relevant by the Investigator should be recorded in the source documents and the AE section of the eCRF.

A local ECG reader will be used.

7.5.1.6 *PHYSICAL EXAMINATION*

Physical examination will be performed at the time points indicated in the [Time and Events Schedule](#).

Physical examination includes height, weight, and waist circumference (height at screening only). To obtain the actual body weight, subjects must be weighed lightly clothed. The height should be measured barefoot. Waist circumference will be measured according to NIH guideline (see [Attachment 5](#)).

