8.2 REMOVAL OF SUBJECTS FROM THE STUDY OR TREATMENT

Subjects have the right to withdraw from the study at any time for any reason, including personal reasons. A subject can withdraw without giving a reason. This will not affect the subject's future care. The Investigator should however try to find out why a subject has withdrawn from the study and document the reason for withdrawal in the source documents and on the eCRF.

A subjects **may** be withdrawn from the study or treatment in the event of:

- An AE, including clinically significant new or worsening existing conditions as judged by the Investigator (documented on the AE Form of the eCRF);
- Subject request (subject moved, schedule conflicts, etc);
- A major protocol violation which would confound interpretation of the results;
- Other: this reason should only be used if the reason for withdrawal is not better accounted for by one of the other categories.

A subjects **must** be withdrawn the study or treatment in the event of:

- Withdrawal of informed consent;
- Lost to follow-up;
- For safety reasons, it being in the best interest of the subject that she be withdrawn, in the Investigator's opinion;
- Development of a medical condition that requires concomitant treatment with a prohibited therapy (see Section [6.2](#));
- Breaking of the randomization code during administration of the study drug by the Investigator or by a member of his/her staff. If the code is broken by the Sponsor, for safety reporting purposes, the subject may remain in the study.
- QT interval corrected according to Fridericia's formula (QTcF) increases to >500 ms, as confirmed by 2 additional ECG recordings obtained within 10 minutes of the initial recording;
- Confirmed decrease in thrombocytes below 75.000, which does not normalize after 7 days;
- ALT or AST >8x ULN;
- ALT or AST >5x ULN for more than 2 weeks;
- ALT or AST >3x ULN and total bilirubin >2x ULN;
- ALT or AST >3xULN with the appearance of fatigue, nausea, vomiting, right upper quadrant pain or tenderness, fever, rash, and/or eosinophilia (>5%).

See [Attachment 6](#) for the procedure to follow in case of suspected drug-induced liver injury (DILI).

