8.3 STOPPING RULES OR DISCONTINUATION CRITERIA

The study may be stopped for any of the following reasons:

- If 2 or more subjects on the study drug are withdrawn from the study due to QTcF interval increases >500 ms, as confirmed by 2 additional ECG recordings obtained within 10 minutes of the initial recording;
- If 2 or more subjects on the study drug are withdrawn from the study due to a confirmed increase in ALT or AST >5x ULN for more than 2 weeks;
- If 2 or more subjects on the study drug are withdrawn from the study due to a confirmed decrease in thrombocytes below 75.000, which does not normalize after 7 days.

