9.1.5 Safety Data

Safety parameters will be tabulated and analyzed descriptively.

Adverse Events

The original terms used in the source documents and the designated sections of the eCRFs by the Investigator to identify AEs will be fully described and coded according to the Medical Dictionary for Regulatory Activities (MedDRA).

The reported AEs will be allocated to phases based on their start date. All AEs will be listed. All AEs with onset during the treatment phase (i.e., TEAEs) will be summarized by treatment arm by System Organ Class (SOC) and Preferred Term (PT).

Special attention will be paid to those subjects who died, discontinued the study drug due to an AE, or experienced a severe or serious AE. Summaries, listings, and narratives (also see Section 12.11) may be provided, as appropriate.

Clinical Laboratory Tests

Each continuous biochemistry and hematology laboratory test will be evaluated by means of descriptive statistics on the actual values, at each assessment time point and by treatment arm. Changes from baseline will be summarized by assessment time point and by treatment arm.

Laboratory tests will be categorized according to the normal ranges of the clinical laboratory (below, within, or above normal). A shift table versus baseline will be created. The worst post-baseline value will be summarized as well.

A listing of subjects with any clinical laboratory test result outside the normal range of the clinical laboratory will be provided.

Vital Signs

Body temperature, pulse rate, SBP, and DBP will be evaluated by means of descriptive statistics (actual values and changes from baseline) and shift tables according to the normal ranges (as defined in [Attachment 7](#)) at each assessment time point and by treatment arm.

Electrocardiogram

Electrocardiogram variables will be evaluated by means of descriptive statistics (actual values and changes from baseline) and shift tables according to the normal ranges (as defined in [Attachment 7](#)) at each assessment time point and by treatment arm.

The ECG variables that will be analyzed are HR, PR interval, QRS interval, QT interval. Values for QTc will be derived. QTcF will be the primary correction parameter [\[31\]](#). Categorical assessment will be performed on absolute QTcF interval prolongation (>450, >480, >500 ms) and on changes from baseline (increase >30 and >60 ms).

Physical Examination

Abnormal findings in physical examination will be listed.

9.1.6 *Interim Analysis*

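### The printed QTcF formula is the inverse of the Fridericia correction it names and is wrong at every heart rate except 60 bpm

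*Protocol*

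**What the plan says.** The Definitions of Terms, after the list of abbreviations, define QTcF as the "QT interval corrected according to Fridericia's formula" and give the expression "QTcF = QT/(1000/RR)^{1/3}". No unit is stated for RR; the constant 1000 implies milliseconds. The formula appears nowhere else in the protocol.

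QTcF is then used in four places:

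- Section 8.2 requires withdrawal when QTcF "increases to >500 ms, as confirmed by 2 additional ECG recordings obtained within 10 minutes of the initial recording".
- Section 8.3 allows the study to be stopped if two or more subjects on study drug are "withdrawn from the study due to QTcF interval increases >500 ms".
- Section 9.1.5 states: "Values for QTc will be derived. QTcF will be the primary correction parameter", citing the original Fridericia paper. It adds: "Categorical assessment will be performed on absolute QTcF interval prolongation (>450, >480, >500 ms) and on changes from baseline", the change categories being increases above 30 and above 60 ms. It also plans shift tables against Attachment 7.
- Attachment 7 sets the normal limit at 450 ms and the normal heart rate at 40 to 100 bpm.

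Section 7.5.1.5 has the investigator or a designee interpret ECGs at the site and adds: "A local ECG reader will be used". It does not say how QTcF is computed there.

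**The concern.** The definition contradicts itself: the words name one correction and the formula gives its reciprocal. The direction can be checked without any outside source. QT shortens as heart rate rises, so standardising to RR = 1000 ms has to lengthen QT when RR is below 1000 ms. The printed expression shortens it further.

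If a site, the eCRF or an analysis program took the formula from the protocol, real prolongation would be hidden above 60 bpm and normal values would be flagged below 60 bpm. The withdrawal rule, the stopping rule that depends on it, the absolute and change categories and the shift table would then rest on wrong values. Because the error changes sign at 60 bpm, no shift of a threshold could compensate for it.

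**Working it through.** There is no stated figure to reproduce, only a formula to compare with the method it names.

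**Inputs.** Printed formula: Definitions of Terms. Thresholds: Sections 8.2, 8.3 and 9.1.5. Heart-rate range of 40 to 100 bpm and 450 ms limit: Attachment 7. RR = 60000/HR in ms. The correct values of 501, 450, 420 and 481 ms below are illustrations; the ratio of printed to correct does not depend on them.

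**Ratio of printed to correct.**

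- Fridericia: F = QT/(RR/1000)^(1/3), so QT = F × (RR/1000)^(1/3).
- Printed: P = QT/(1000/RR)^(1/3) = QT × (RR/1000)^(1/3).
- Hence P = F × (RR/1000)^(2/3) = F × (60/HR)^(2/3), and the two agree only at 60 bpm.

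| HR (bpm) | RR (ms) | P/F | Correct 501 ms reads as | Correct value that reads as 500 ms |
|---|---|---|---|---|
| 40 | 1500 | 1.310 | 656 | 382 |
| 50 | 1200 | 1.129 | 566 | 443 |
| 60 | 1000 | 1.000 | 501 | 500 |
| 65 | 923 | 0.948 | 475 | 527 |
| 75 | 800 | 0.862 | 432 | 580 |
| 90 | 667 | 0.763 | 382 | 655 |
| 100 | 600 | 0.711 | 356 | 703 |

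**Where decisions flip.**

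- A correct 501 ms reads 500 ms or less from 60 × (501/500)^1.5 = 60.2 bpm upward.
- It reads 450 ms or less, normal under Attachment 7, from 60 × (501/450)^1.5 = 70.5 bpm upward.
- A correct 450 ms reads above 500 ms below 60 × (450/500)^1.5 = 51.2 bpm.

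**Changes from baseline.**

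- Correct QTcF constant at 420 ms, heart rate falling from 75 to 66 bpm: 420 × (60/66)^(2/3) − 420 × (60/75)^(2/3) = 394.1 − 361.9 = +32.2 ms. This false rise enters the >30 ms category.
- Correct QTcF rising from 420 to 481 ms at a steady 75 bpm: 61 × 0.8618 = +52.6 ms. A true rise of 61 ms misses the >60 ms category.

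**Could RR be in seconds?** A correct 501 ms at 75 bpm corresponds to QT = 501 × 0.8^(1/3) = 465.1 ms. The printed form with RR = 0.8 s gives 465.1/(1000/0.8)^(1/3) = 43.2 ms, which is not a usable value. The choice of unit does not rescue the formula.

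**The case against.** The strongest reply is that this is a notation slip in a glossary. The withdrawal rule and Section 9.1.5 name Fridericia's method or cite its source, and neither refers the reader to the printed expression. ECG software and the CRO's SAS programs may well use the right formula. The glossary line differs from a correct multiplicative form by one operator, so a fault in text conversion cannot be fully excluded. That makes a look at the sponsor's source file worthwhile, but the expression is complete and well formed as it stands.

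Much of the reply on reach also stands. Section 9.1.5 analyses QT and heart rate as variables, so every table could be recomputed. By the Time and Events Schedule, ECGs are recorded at screening and at Visits 2, 3, 5 and 6. The Visit 2 ECG precedes the first dose, Visit 5 is the end of treatment apart from up to 4 further days of dosing if DEXA is late, and Visit 6 is after treatment. On scheduled ECGs, a missed withdrawal would therefore matter mainly at Week 4. The investigator can also withdraw a subject on safety grounds whatever the formula gives, and the stopping rule is permissive. Section 1.2.3 reports no significant hERG inhibition and no QTc effect in monkeys, and Section 1.3 reports no clinically relevant ECG trend in Phase I.

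These points lower the chance and extent of harm. They do not make the definition right. Nothing else in the protocol restates the formula, Section 7.5.1.5 does not say how sites compute QTcF, and Section 1.5 describes knowledge of the side-effect profile as still limited.

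**Conclusion.** The concern holds. The printed definition is the inverse of the correction it names and is wrong at every heart rate but 60 bpm, by a factor of 1.31 to 0.71 across the protocol's own normal range. The arithmetic assumes only that RR is in milliseconds.

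The consequence is conditional: it arises if the printed line is implemented, and the protocol does not show that anyone will do so. In that case the ECG tables would be wrong but repairable, while a missed mandatory withdrawal during dosing would not be. No bias towards either arm is claimed, and the primary efficacy analysis is unaffected. The definition should be corrected because it sits under a mandatory safety rule and correcting it has no downside.

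**What to change.** Replace the expression in the Definitions of Terms by QTcF = QT/(RR/1000)^(1/3), with RR in ms, or equivalently QT × (1000/RR)^(1/3), and state the unit. Confirm that site ECG decisions, the eCRF derivation and the SAS programs use this form. A test record with QT 400 ms at 75 bpm should give 430.9 ms; the inverted form gives 371.3 ms. Leave all thresholds as they are. The cost is one line of text and a check of the derivations, with no new data.

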1.2 NON-CLINICAL STUDIES

1.2.1 *Summary of Pharmacodynamics*

Pharmacological assays characterized ESN364 as an NK3 receptor antagonist with activity to lower sex hormones via a reduction in LH, indicative of a centrally-mediated effect. *In vitro* studies demonstrated that ESN364 is a potent full inhibitor of human neurokinin (hNK) 3 receptor and is highly selective for hNK3 in comparison to the other members of tachykinin receptor family (hNK1 and hNK2) and other G-protein coupled receptors including the ones known to be implicated in modulation of GnRH axis. Further *in vitro* studies demonstrated that ESN364 have similar affinity for *human* and *monkey* NK3 receptors. The ESN364 affinity for *rat* NK3 receptor was high, however 8-fold less than the affinity for *human* NK3 receptor. These data indicated that rat and specially monkey are useful animal models for *in vivo* non-clinical testing.

In vivo studies demonstrated that ESN364 significantly reduces plasma LH levels in castrate male rats at a dose range of 3 to 20 mg/kg. At a dosage of 3 mg/kg, ESN364 significantly reduced circulating testosterone levels in intact male rats. ESN364 effectively reduced prostate size without concomitant effects to reduce testis weight in rat model of benign prostate hyperplasia (BPH) at dosages of 10 and 30 mg/kg (once daily [q.d.]; oral administration) after 21 days of treatment.

In ovariectomized female rats, ESN364 significantly reduced the mean plasma levels and pulsatile LH secretion frequency and amplitude at 10 mg/kg dosage. ESN364 treatment at the dosage of 10 mg/kg twice daily (b.i.d.) for a period of 10 days reduced E2 levels and appeared to prolong the estrous cycle in adult intact female rats. ESN364 significantly reduced circulating LH levels in castrate male monkeys following single and 5-day repeated oral dosing at 5 mg/kg/day. After five consecutive days of dosing, ESN364 had no effect on plasma FSH levels, demonstrating that antagonism of the NK3 receptor is a means to selectively inhibit LH, but not FSH, as a novel and precise approach to modulate the HPG axis for the treatment of sex hormone disorders.

ESN364 suppressed plasma LH levels 2 hours following bolus injection in ovariectomized female ewes at the 1 mg/kg dosage; pulsatile LH secretion restored

2-4 hours after the injection. ESN364 injection had no effect on FSH secretion in ovariectomized female ewes.

ESN364 significantly reduced LH, E2, and progesterone (P4) levels in intact Cynomolgus female monkeys after oral administration at the dosages of 10, 25 and 50 mg/kg/day during a treatment period of 35 days. The reduction in E2 was not to castration levels. With the same dosages and duration in female monkeys, ESN364 had no effect on FSH and testosterone levels. The LH, E2, and P4 levels were recovered in all compound treated animals after 28 days following cessation of treatment. In intact male Cynomolgus monkeys, following oral administration of ESN364 at the dosages of 25 and 50 mg/kg/day, there was a small trend towards decrease levels of mean testosterone, LH and E2, whereas no test item-related effects were seen on male FSH levels.

1.2.2 *Summary of Pharmacokinetics*

Pharmacokinetic (PK) and absorption, distribution, metabolism, and elimination (ADME) studies have been performed to demonstrate that ESN364 has a suitable profile for continued advancement through preclinical development as an oral product for the treatment of sex-hormone related disorders.

Following oral administration of ESN364 at a dose range of 3 to 20 mg/kg in castrate male rats, plasma concentrations increased linearly with dose and remained stable up to 300 minutes. ESN364 in methylcellulose formulation (0.5%) showed a good oral absorption in intact male rats at dosage of 3 mg/kg. In a BPH rat model, administration of ESN364 at dosages of 3, 10, 30 mg/kg q.d. (oral administration) for 21 days showed no significant accumulation, high absorption variability with relatively well-respected absorption ratios between the doses.

ESN364 had a rapid oral absorption after 1.0 hour postdose with a maximum plasma concentration within 5.0 hours postdose in monkeys at dosages of 10, 25 and 50 mg/kg. There was little or no accumulation of ESN364 following repeated dose administration for 25 days. There were no notable trends in the plasma concentrations or toxicokinetic parameters which could be related to gender.

ESN364 was devoid of significant inhibition of cytochrome P (CYP) 450 enzymes (>40 μ M, standard panel). Plasma protein binding was low (<50%) and microsome stability was high ($t_{1/2} > 1000$ min) with consistent values in matrices from rat, monkey and human. Also, metabolic stability in hepatocytes proved to be similar across species (rat, monkey, human).

ESN364 had a good PK profile in rats with a low clearance, a good exposure, an elimination half-life longer than 4.0 hours, and bioavailability consistent with potential use via oral administration. Pharmacokinetic studies in rats and monkeys indicated that ESN364 undergoes low clearance and exhibits high oral exposure. In rats and monkeys, a single metabolite was predominantly observed resulting from an oxidation. The main route of excretion in both species was in the urine, with the oxidized metabolite being more rapidly excreted. Thus, the PK and excretory pathways appeared similar in rats and monkeys, the two species selected as models for the human safety profiling of this product.

High brain penetration was demonstrated in rat, consistent with the putative central mechanism of action of ESN364 to regulate LH release.

Toxicokinetic studies in rats showed that mean plasma concentrations are at a maximum at between 1.0 and 8.0 hours postdose for both males and females in all dosage groups (30, 100, 300 mg/kg/day; oral administration). Exposure of ESN364 indicated no accumulation and appeared to be similar in males and females on both sampling occasions and at all dose levels.

Toxicokinetic studies in monkeys demonstrated that ESN364 had a rapid oral absorption after 1.0 hour postdose (10, 25, 50 mg/kg/day; oral administration) with a maximum plasma concentration within 5.0 hours postdose. There was little or no accumulation of ESN364 following repeated dose administration for 25 days. There were no notable trends in the plasma concentrations or toxicokinetic parameters which could be related to gender.

1.2.3 Summary of Toxicology

No cytotoxicity was observed for ESN364 using HEPG2 cells. ESN364 did not induce mutation in 5 histidine-requiring strains of *Salmonella typhimurium* (TA98, TA100, TA1535, TA1537, and TA102) in the absence and in the presence of a rat liver metabolic activation system S9. ESN364 did not induce chromosome aberrations in cultured human peripheral blood lymphocytes up to a concentration equivalent to 1 mM for 3+17 hours in the absence and presence of S9 and for 20+0 hours in the absence of S9.

ESN364 did not exhibit any significant inhibition of human ether-à-go-go-related gene (hERG) channels nor did it significantly modulate either the electrical or the mechanical properties of the heart in a Langendorff model (rabbit) at tested concentrations up to 30 μ M. In the human embryonic kidney (HEK) 293 cells transfected with hERG, ESN364 exhibited a hERG inhibition liability which was more than 8000-fold lower than that of the reference compound (terfenadine).

A study to investigate the effect of ESN364 on general activity, behavior and body temperature, oral administration of ESN364 to male and female Han Wistar rats demonstrated signs associated with sedation together with constricted pupils at the dose level of 250 mg/kg. At the dose level of 125 mg/kg, constricted pupils was the only sign seen and was present in 50% of the animals. These signs were judged to be of mild intensity and showed complete recovery at 24 hours postdose. No significant effect on body temperature was observed.

Measurement of respiratory parameters using whole body plethysmography in rats showed a clear dose-related response in both male and female rats with minimal transient effects at the low dose (40 mg/kg) and increasing marked effects on tidal volume with increasing dose levels (80 and 125 mg/kg). In the context of this study, and the absence of respiratory-related clinical signs, the respiratory effects were not considered to be adverse.

Electrocardiographic investigations in conscious male Cynomolgus monkeys showed that single oral doses of ESN364 at 10, 25, and 50 mg/kg were well-tolerated and elicited no significant changes. A slight decrease in mean $+dP/dt_{max}$ and systolic and mean arterial blood pressure as well as a slight increase in heart rate (HR) were observed. No electrocardiogram (ECG) waveform morphologic abnormalities on qualitative

assessments and no effects on PR, QRS, and QTc (QT interval corrected for heart rate) interval following oral doses of ESN364 were noted.

Repeated-dose toxicity studies in male and female HsdHan™: Wist rats demonstrate that daily oral administration of ESN364 for 28 days at dose levels of 30 and 100 mg/kg was well-tolerated. At the highest daily dosage of 300 mg/kg, two deaths and marked clinical signs (lethargy, reduced activity, labored respiration and staggering) and body weight loss during the first few days of treatment were observed. There were histopathological findings in the 100 and 300 mg/kg dosing groups in the lung, liver, bone marrow, uterus, ovary and prostate and some with corresponding changes in weight and macroscopic evaluation. These changes were considered to be adaptive or related to the pharmacology of the test article rather than being an adverse effect. Based on the findings from this study, the No observed adverse effect level (NOAEL) was considered to be 100 mg/kg/day in rats.

Repeated-dose toxicity studies in male and female Cynomolgus monkeys showed that daily oral administration of ESN364 for 5 weeks up to a dose of 50 mg/kg/day was tolerated with no mortality and no test item-related effects on hematology, clinical chemistry, urinalysis, respiratory rate, neurobehavioral observations, ophthalmic examinations, cardiovascular investigations and organ weights. Following oral administration of ESN364, a loss of body weight was observed, especially in male monkeys. One female monkey in the 50 mg/kg dosing group showed hyperplasia of lymphocytes in lymph nodes, spleen and lung and perivascular inflammation in the kidney. Therefore, the NOAEL for ESN364 was defined to be 25 mg/kg/day in monkeys.

For more detailed information on ESN364 and the conducted long-term (13-week) toxicology studies, refer to the current Investigator's Brochure [\[14\]](#).

